7.2.2 SAE reporting

To ensure patient safety, every SAE, regardless of causality, occurring after the patient has provided informed consent and until 30 days after the last study visit (Visit 405) must be reported to Novartis within 24 hours of learning of its occurrence. Any SAEs experienced after the 30 day period should only be reported to Novartis if the investigator suspects a causal relationship to study treatment.

Recurrent episodes, complications, or progression of the initial SAE must be reported as follow-up to the original episode, regardless of when the event occurs. This report must be submitted within 24 hours of the investigator receiving the follow-up information. An SAE that is considered completely unrelated to a previously reported one should be reported separately as a new event.

[figure not shown]
Information about all SAEs (either initial or follow-up information) is collected and recorded in English on the paper Serious Adverse Event Report Form or the electronic Serious Adverse Event Form within the Oracle Clinical/Remote Data Capture (OC/RDC) system (where available). The investigator must assess the relationship to each specific component of the study treatment (if the study treatment consists of several components).

SAEs (initial and follow-up) that are recorded on the paper SAE form should be faxed within 24 hours of awareness of the SAE to the local Novartis Drug Safety and Epidemiology Department. The telephone and fax number of the contact persons in the local department of Drug Safety and Epidemiology, specific to the site, are listed in the investigator folder provided to each site. The original copy of the SAE Report Form and the fax confirmation sheet must be kept with the case report form documentation at the study site. Follow-up information should be provided using a new paper SAE Report Form stating that this is a follow-up to a previously reported SAE.

SAEs (initial and follow-up) that are recorded electronically in the OC/RDC system should be entered, saved and e-signed within 24 hours of awareness of the SAE or changes to an existing SAE. These data will automatically be submitted to Novartis Drug Safety & Epidemiology immediately after investigator signature or 24 hours after entry, whichever occurs first.

Follow-up information provided should describe whether the event has resolved or continues, if and how it was treated and whether the patient continued or withdrew from study participation. Each re-occurrence, complication, or progression of the original event should be reported as a follow-up to that event regardless of when it occurs.

If the SAE is not previously documented in the Investigator's Brochure or Package Insert (new occurrence) and is thought to be related to the investigational treatment a Drug Safety and Epidemiology Department associate may urgently require further information from the investigator for Health Authority reporting. Novartis may need to issue an Investigator Notification (IN) to inform all investigators involved in any study with the same investigational treatment that this SAE has been reported. Suspected Unexpected Serious Adverse Reactions (SUSARs) will be collected and reported to the competent authorities and

relevant ethics committees in accordance with EU Guidance 2011/C 172/01 or as per national regulatory requirements in participating countries.

7.3 Liver safety monitoring

To ensure patient safety and enhance reliability in determining the hepatotoxic potential of an investigational drug, a standardized process for identification, monitoring and evaluation of liver events has to be followed.

The following two categories of abnormalities / adverse events have to be considered during the course of the study:

- Liver laboratory triggers, which will require repeated assessments of the abnormal laboratory parameter
- Liver events, which will require close observation, follow-up monitoring and completion of the standard base liver CRF pages

Please refer to [Table 13-1](#) in [Appendix 2](#) for complete definitions of liver laboratory triggers and liver events.

Every liver laboratory trigger or liver event as defined in [Table 13-1](#) of [Appendix 2](#) should be followed up by the investigator or designated personal at the trial site as summarized below. Detailed information is outlined in [Table 13-2](#) in [Appendix 2](#).

For the liver laboratory trigger:

- Repeating the LFT within the next week to confirm elevation.

[figure not shown]
These LFT repeats should be performed using the central laboratory if possible. If this is not possible, then the repeats can be performed at a local laboratory to monitor the safety of the patient. Repeats laboratory should then be performed at central laboratory as soon as possible. If a liver event is subsequently reported, any local LFTs previously conducted that are associated with this event should be reported on the Liver CRF pages.

- If the elevation is confirmed, close observation of the patient will be initiated, including consideration of treatment interruption if deemed appropriate.

For the liver events:

- Repeating the LFT to confirm elevation as appropriate
- Discontinuation of the investigational drug if appropriate
- Hospitalization of the patient if appropriate
- A causality assessment of the liver event via exclusion of alternative causes (e.g., disease, co-medications)
- An investigation of the liver event which needs to be followed until resolution.

These investigations can include serology tests, imaging and pathology assessments, hepatologist's consultancy, based on investigator's discretion. All follow-up information, and the procedures performed should be recorded on appropriate CRF pages, including the liver event overview CRF pages.

7.4 Renal safety monitoring

To ensure patient safety and enhance reliability in determining the nephrotoxic potential of an investigational drug, a standardized process for identification, monitoring and evaluation of renal events has to be followed.

The following two categories of renal adverse events have to be considered during the course of the study:

1. Serum event:
 - confirmed (after ≥ 24 h) increase in serum creatinine of $\geq 25\%$ compared to baseline during normal hydration status
2. Urine event:
 - New onset ($\geq 1+$) proteinuria, hematuria or glucosuria; or
 - Doubling in the urinary albumin-creatinine ratio (ACR) or urinary protein-creatinine ratio (PCR) (if applicable).

Every renal laboratory trigger or renal event as defined in [Table 7-1](#) should be followed-up by the investigator or designated personnel at the trial site as summarized below.

Table 7-1 Specific Renal Alert Criteria and Actions

Serum Event	
Serum creatinine increase 25-49% compared to baseline	Confirm 25% increase after 24-48h Follow-up within 2-5 days
Acute Kidney Injury: Serum creatinine increase $\geq 50\%$ compared to baseline	Follow-up within 24-48h if possible Consider drug interruption Consider patient hospitalization/specialized treatment
Urine Event	
New dipstick proteinuria $\geq 1+$	Confirm value after 24-48h
Albumin- or Protein-creatinine ratio increase ≥ 2 -fold	Perform urine microscopy
Albumin-creatinine ratio (ACR) ≥ 30 mg/g or ≥ 3 mg/mmol	Consider drug interruption/discontinuation
Protein-creatinine ratio (PCR) ≥ 150 mg/g or >15 mg/mmol	
New dipstick glucosuria $\geq 1+$ not due to diabetes	Blood glucose (fasting) Perform serum creatinine, ACR
New dipstick hematuria $\geq 1+$ not due to trauma	Urine sediment microscopy Perform serum creatinine, ACR
For all renal events:	
1. Document contributing factors in the CRF : co-medication, other co-morbid conditions, and additional diagnostic procedures performed	
2. Monitor patient regularly (frequency at investigator's discretion) until either: Event resolution : sCr within 10% of baseline or protein-creatinine ratio within 50% of baseline, or Event stabilization : sCr level with $\pm 10\%$ variability over last 6 months or protein-creatinine ratio stabilization at a new level with $\pm 50\%$ variability over last 6 months.	

7.5 Reporting of study treatment errors including misuse/ abuse

Medication errors are unintentional errors in the prescribing, dispensing, administration or monitoring of study drug while under the control of a healthcare professional, patient or consumer

Misuse refers to situations where the medicinal product is intentionally and inappropriately used not in accordance with the protocol.

Abuse corresponds to the persistent or sporadic intentional excessive use of a medicinal product which is accompanied by harmful physical or psychological effects.

Study treatment errors and uses outside of what is foreseen in the protocol will be collected in the DAR (dose administration record) eCRF irrespective of whether or not associated with an AE/SAE and reported to safety only if associated with an SAE. Misuse or abuse will be collected and reported in the safety database irrespective of it being associated with an AE/SAE

Table 7-2 Reporting of study treatment errors

Treatment error type	Document in Dose Administration (DAR) eCRF (Yes/ No)	Document in AE eCRF	Complete SAE form
Unintentional study treatment error	Yes	Only if associated with an AE	Only if associated with an SAE
Misuse/ Abuse	Yes	Yes	Yes even if not associated with an SAE

7.6 Pregnancy reporting

[figure not shown]
To ensure patient safety, each pregnancy occurring while the patient is on study treatment must be reported to Novartis within 24 hours of learning of its occurrence. The pregnancy should be followed-up to determine outcome, including spontaneous or voluntary termination, details of the birth, and the presence or absence of any birth defects, congenital abnormalities, or maternal and/or newborn complications.

Pregnancy should be recorded on the Pharmacovigilance Pregnancy Form and reported by the investigator to the local Novartis Drug Safety and Epidemiology Department. Pregnancy follow-up should be recorded on the same form and should include an assessment of the possible relationship to the study treatment.

Any SAE experienced during the pregnancy and unrelated to the pregnancy must be reported on a SAE form.

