- No study treatment will be given during the post-treatment follow-up epoch; however, patients are allowed to take background medication and rescue medication. If a subject relapses i.e. develops symptoms with an UAS7 ≥ 12 , the investigator should be contacted for an ad-hoc visit to consider treatment with standard of care or other therapy.

Figure 3-1 Study design

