3.2 Rationale of study design

An open-label study design was chosen to obtain information on the long-term safety and efficacy of QGE031 (240 mg) given s.c. q4w for 52 weeks in patients with chronic spontaneous urticaria patients completing study CQGE031C2201. An open-label design avoids exposing patients to placebo for an extended period of time and administration of QGE031 240 mg allows for maximum exposure to the study drug. The 48-week post-treatment follow-up epoch will assess safety following treatment discontinuation, as well as to evaluate [REDACTED] including sustained remission.

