5.6 Study completion and discontinuation

5.6.1 Study completion and post study treatment

Study completion for individual patients will be when he/she has completed the extension study 52 weeks of treatment and the full follow-up epoch up to and including Visit 405.

Treatment completion will be when the patient completed the full 52-week treatment epoch. If patients relapse during the follow-up epoch of the extension study as defined by a UAS7 \geq 12, they will be allowed to exit the study if desired and receive conventional therapy at the discretion of the investigator.

Completion of the study will be considered when all patients will have completed 52 weeks of treatment epoch and the full follow up epoch or have prematurely withdrawn from the study.

Information on the subject's completion or discontinuation of the study and the reason for discontinuation of the study will be recorded on the appropriate Study Epoch Completion eCRF page.

When the patient has completed all scheduled study assessments, the investigator must call or logon to the IRT system to record the patient completion as per above completion definitions.

The following is recommended for initiating other treatment outside or post study:

- A wash-out of QGE031 of at least 4 months is advised prior to commencing Xolair® treatment

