6.5.6 Pregnancy

Women of child-bearing potential only will have a urine pregnancy test at the visits specified in [Table 6-1](#). A positive urine pregnancy test requires a serum sample to be sent to the Central Lab and, during treatment epoch, immediate interruption of study medication until serum β -hCG is performed and found to be negative. If positive, the patient must be discontinued from the study drug but remain on the trial for the safety evaluation. Urine pregnancy test kits will be provided to the sites by the Central Lab.

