7.2 Serious adverse events

7.2.1 Definition of SAE

An SAE is defined as any adverse event (appearance of (or worsening of any pre-existing) undesirable sign(s), symptom(s) or medical conditions(s) which meets any one of the following criteria:

- is fatal or life-threatening
- results in persistent or significant disability/incapacity
- constitutes a congenital anomaly/birth defect
- requires inpatient hospitalization or prolongation of existing hospitalization, unless hospitalization is for:
 - routine treatment or monitoring of the studied indication, not associated with any deterioration in condition (specify what this includes)
 - elective or pre-planned treatment for a pre-existing condition that is unrelated to the indication under study and has not worsened since signing the informed consent
 - treatment on an emergency outpatient basis for an event not fulfilling any of the definitions of a SAE given above and not resulting in hospital admission
 - social reasons and respite care in the absence of any deterioration in the patient's general condition
- is medically significant, i.e. defined as an event that jeopardizes the patient or may require medical or surgical intervention.

[figure not shown]
All malignant neoplasms will be assessed as serious under “medically significant” if other seriousness criteria are not met.

Life-threatening in the context of a SAE refers to a reaction in which the patient was at risk of death at the time of the reaction; it does not refer to a reaction that hypothetically might have caused death if more severe (see Annex IV, ICH-E2D Guideline).

Medical and scientific judgment should be exercised in deciding whether other situations should be considered serious reactions, such as important medical events that might not be immediately life threatening or result in death or hospitalization but might jeopardize the patient or might require intervention to prevent one of the other outcomes listed above. Examples of such events are intensive treatment in an emergency room or at home for allergic bronchospasm, blood dyscrasias or convulsions that do not result in hospitalization or development of dependency or abuse (see Annex IV, ICH-E2D Guideline).

Any suspected transmission via a medicinal product of an infectious agent is also considered a serious adverse reaction.

All AEs (serious and non-serious) are captured on the CRF, SAEs also require individual reporting to DS&E as per [section 7.2.2](#)

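### Pregnancy notification and outcome follow-up (Protocol 7.6) are tied to time on study treatment, so pregnancies conceived in the 48-week follow-up are not clearly covered, although testing continues to Visit 405

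*Protocol*

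**What the plan says.** **Reporting rule.** Under Protocol 7.6, "each pregnancy occurring while the patient is on study treatment must be reported to Novartis within 24 hours of learning of its occurrence". The next sentence asks that the pregnancy be followed to its outcome. A second paragraph adds: "Pregnancy should be recorded on the Pharmacovigilance Pregnancy Form and reported by the investigator to the local Novartis Drug Safety and Epidemiology Department". That paragraph states no period of its own.

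**When treatment ends.** Protocol 3.1 puts the last dose at Visit 313 and says: "No study treatment will be given during the post-treatment follow-up epoch". Protocol 5.6.1 says: "Treatment completion will be when the patient completed the full 52-week treatment epoch". SAP 2.1.5 ends exposure 28 days after the last dose.

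**What continues afterwards.** Protocol 6.5.6 provides that "Women of child-bearing potential only will have a urine pregnancy test at the visits specified in" Table 6-1, and that table marks the test at all five follow-up visits, 401 to 405. A positive urine test needs serum confirmation in any epoch. The instructions on stopping drug are tied to the treatment epoch, and 6.5.6 names no notification step. Protocol 3.2 gives the purpose of the period: "The 48-week post-treatment follow-up epoch will assess safety following treatment discontinuation".

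**SAE backstop.** Protocol 7.2.1 counts as serious an event that "constitutes a congenital anomaly/birth defect". Under 7.2.2 every SAE from consent "until 30 days after the last study visit (Visit 405) must be reported to Novartis within 24 hours", whatever its cause. After that, reporting depends on the investigator suspecting the drug.

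**Contraception.** Exclusion criterion 18 asks for contraception during dosing. Protocol 10.2 asks for it throughout the study.

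**The concern.** The protocol keeps looking for pregnancies for 48 weeks after treatment but does not clearly say what follows from finding one. A site that confirms a pregnancy conceived in follow-up can read 7.6 literally and conclude that it owes the sponsor neither a 24-hour report nor an outcome.

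This is a long-term safety study, follow-up is part of the safety assessment, and Protocol 10.2 itself warns of unknown fetal risk from a pregnancy during the study. What could be lost is the outcome of pregnancies that begin soon after the last dose and, for later conceptions, unconditional reporting of birth defects. The study's efficacy and safety summaries do not depend on these data.

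**Working it through.** **Inputs from the documents** (patient completing treatment; days from Table 6-1 and SAP Table 1-1)
- Last dose, Visit 313: Day 337
- Start of follow-up, Visit 401: Day 365
- Last visit, Visit 405: Day 701
- Treatment-emergent window: 16 weeks (112 days) after the last dose in SAP 2.5.1; 52 weeks (364 days) in Protocol 9.4.1
- SAE reporting: to 30 days after Visit 405

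**Assumptions, not in the documents**
- Conception to birth: 245 to 280 days
- Women of child-bearing potential: 60 to 150
- Pregnancy rate: 1 to 5 per 100 woman-years, no dropout

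**1. The plan's own figure.** (701 − 365) / 7 = 336 / 7 = 48 weeks, which reproduces the stated length of follow-up. Last dose plus 28 days is 337 + 28 = Day 365, so the end of exposure in the SAP coincides with the start of follow-up.

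**2. Days not clearly covered.** 701 − 365 = 336 days, containing five scheduled pregnancy tests (Days 365, 449, 533, 617 and 701).

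**3. Overlap with the treatment-emergent windows.**
- SAP: 337 + 112 = Day 449, and 449 − 365 = 84 follow-up days are inside.
- Protocol: 337 + 364 = Day 701, so all of follow-up is inside.

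**4. Reach of the SAE backstop.**
- The window closes at 701 + 30 = Day 731.
- A conception on Day 449 delivers between 449 + 245 = Day 694 and 449 + 280 = Day 729, both before Day 731. A birth defect recognised at birth is therefore a reportable SAE for every conception in the 84 days.
- The latest conception delivering by Day 731 falls between 731 − 280 = Day 451 and 731 − 245 = Day 486.
- Conceptions in the last 701 − 486 = 215 to 701 − 451 = 250 days deliver after Day 731. For these, a birth defect is reportable only if the investigator suspects the drug.

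**5. Expected pregnancies** = women × (days / 365) × rate.

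| Period | Low | High |
|---|---|---|
| 336 days | 60 × 336/365 × 0.01 = 0.55 | 150 × 336/365 × 0.05 = 6.90 |
| 84 days | 60 × 84/365 × 0.01 = 0.14 | 150 × 84/365 × 0.05 = 1.73 |

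**The case against.** The strongest reply is that the second paragraph of 7.6 carries no treatment qualifier, so a careful site would complete the form for any pregnancy. That reading is possible, which is why the gap is described as unclear coverage and not as an outright omission. But the paragraph mainly names the form and the recipient, and it follows directly on a sentence limited to time on treatment. Read broadly, it would leave that limit with little to do.

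Second, the sponsor would see a positive test anyway: the result goes on the CRF, the serum sample goes to the central laboratory (6.5.6), and laboratory results are transferred electronically (8.3). This stands as a route to awareness. It is not a 24-hour report, and it does not oblige anyone to determine the outcome.

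Third, the two harms do not overlap. Conceptions inside the 16-week window still have the SAE backstop for a birth defect seen at birth, and those without it begin after Day 451, outside that window. This is correct. Inside the 84 days, what is missing is notification and outcomes that are not SAEs. The SAE rule also helps only if the site learns of the defect, and nothing clearly requires it to follow the pregnancy.

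Fourth, only 84 of the 336 days are drug-relevant on the SAP's window, which was written for tabulating adverse events. However, the protocol's own treatment-emergent definition (9.4.1) spans all of follow-up, and 5.6.1 advises a wash-out of at least 4 months before omalizumab.

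Finally, the expected counts rest on assumptions. Patients who relapse may leave follow-up, and contraception is asked for throughout the study under 10.2, so the upper figure is probably generous.

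**Conclusion.** The concern holds. Followed literally, 7.6 leaves pregnancies conceived after treatment without a clear duty of notification or outcome follow-up for up to 336 days in a patient who completes treatment. A stricter reading that ends treatment at the last dose would start the gap earlier, at Day 337.

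Pregnancies conceived on treatment are covered whenever they are detected, and SAEs, including birth defects known to the site, are reportable to Day 731. The remaining gap is modest: probably a handful of pregnancies at most, on assumed numbers. The change should be made because it is a specific safety gain at small cost. Confidence is medium, because the conclusion depends on how the second paragraph of 7.6 and the undefined term for being on treatment are read.

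**What to change.** In 7.6, replace the on-treatment qualifier with a stated period running from the first extension dose through Visit 405, or at minimum through 16 weeks after the last dose. The minimum version would add the 84 days to Day 449 and leave 701 − 449 = 252 days of follow-up outside. State that the outcome is to be determined for every pregnancy in that period, on the existing pregnancy form. In the same amendment, bring the contraception period in exclusion criterion 18 into line with 10.2.

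The cost is a written amendment with the approvals set out in 11.1, plus outcome follow-up of a few pregnancies, some of it after Visit 405. The tests, visits and form are already in place.

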7.7 Prospective suicidality assessment

All SAEs relating to suicidal behavior should be reviewed by the Safety Management Team or early project teams.

8 Data review and database management

8.1 Site monitoring

Before study initiation, at a site initiation visit or at an investigator's meeting, a Novartis representative will review the protocol and CRFs with the investigators and their staff. During the study, Novartis employs several methods of ensuring protocol and GCP compliance and the quality/integrity of the sites' data. The field monitor will visit the site to check the completeness of patient records, the accuracy of entries on the eCRFs, the adherence to the protocol and to Good Clinical Practice, the progress of enrollment. The study monitor will also ensure that study drug is being stored, dispensed, and accounted for according to specifications. Key study personnel must be available to assist the field monitor during these visits. Continuous remote monitoring of each site's data may be performed by a centralized Novartis CRA organization. Additionally, a central analytics organization may analyze data and identify risks and trends for site operational parameters, and provide reports to Novartis Clinical Teams to assist with trial oversight.

[figure not shown]
The investigator must maintain source documents for each patient in the study, consisting of case and visit notes (hospital or clinic medical records) containing demographic and medical information, laboratory data, electrocardiograms, and the results of any other tests or assessments. All information on CRFs must be traceable to these source documents in the patient's file. The investigator must also keep the original informed consent form signed by the patient (a signed copy is given to the patient).

The investigator must give the monitor access to all relevant source documents to confirm their consistency with the CRF entries. Novartis monitoring standards require full verification for the presence of informed consent, adherence to the inclusion/exclusion criteria, documentation of SAEs, and of data that will be used for all primary variables. Additional checks of the consistency of the source data with the CRFs are performed according to the study-specific monitoring plan. No information in source documents about the identity of the patients will be disclosed.

